9.1 Identity of Trial Product: Rabies Vaccine

Vaccine: RabAvert® (Rabies Vaccine) produced by Novartis Vaccines and Diagnostics GmbH is a sterile freeze-dried vaccine obtained by growing the fixed-virus strain Flury LEP in primary cultures of chicken fibroblasts. The strain Flury LEP was obtained from American Type Culture Collection as the 59th egg passage. The growth medium for propagation of the virus is a synthetic cell culture medium with the addition of human albumin, polygeline (processed bovine gelatin) and antibiotics. The virus is inactivated with β -propiolactone, and further processed by zonal centrifugation in sucrose density-gradient. The vaccine is lyophilized after addition of a stabilizer solution that consists of buffered polygeline and potassium glutamate. One dose of reconstituted vaccine contains less than 12 mg polygeline (processed bovine gelatin), less than 0.3 mg human serum albumin, 1 mg potassium glutamate and 0.3 mg sodium EDTA. Small quantities of bovine serum are used in the cell culture process. Bovine components originate only from the United States, Australia and New Zealand. Minimal amounts of chicken protein may be present in the final product; ovalbumin content is less than 3 ng/dose (1 mL), based on ELISA. In the final vaccine, neomycin is present at < 1 μ g, chlortetracycline at < 20 ng, and amphotericin B at < 2 ng per dose. RabAvert® is intended for intramuscular (IM) injection. The vaccine contains no preservative and should be used immediately after reconstitution with the supplied Sterile Diluent for RabAvert® (Water for Injection). The potency of the final product is determined by the US National Institute of Health (NIH) mouse potency test using the US reference standard. The potency of one dose (1.0 mL) RabAvert® is at least 2.5 IU of rabies antigen. RabAvert® is a white, freeze-dried vaccine for reconstitution with the water for injection diluent prior to use; the reconstituted vaccine is a clear to slightly opaque, colorless solution.

Form:	Powder and solvent for suspension for injection
Dose:	1.0 ml of the reconstituted vaccine
Route:	ID/IM
Batch number:	To be determined

9.1.1 Composition

RabAvert® (Rabies Vaccine) produced by Novartis Vaccines and Diagnostics GmbH is a sterile freeze-dried vaccine obtained by growing the fixed-virus strain Flury LEP in primary cultures of chicken fibroblasts. The strain Flury LEP was obtained from American Type Culture Collection as the 59th egg passage. The growth medium for propagation of the virus is a synthetic cell culture medium with the addition of human albumin, polygeline (processed bovine gelatin) and antibiotics. The virus is inactivated with β -propiolactone, and further processed by zonal centrifugation in a sucrose density-gradient. The vaccine is lyophilized after addition of a stabilizer solution which consists of buffered polygeline and potassium glutamate.

Placebo: Human Serum Albumin 0.03%. Produced by Greer Labs, for use as a sterile diluent.

Form:	Diluent
Dose:	1.0 ml of diluent
Route:	IM/ID
Batch/ Lot number:	To be determined

9.1.2 Preparation and Administration

The vaccine comes as powder and reconstituted for injection. Vaccine will be administered by ID in the forearm or IM injection in the deltoid.

9.1.3 Dose Selection and Timing

The dose for IM vaccinations will be 1 ml for each vaccination. The dose for ID vaccinations will be 0.1 ml for each vaccination. Two vaccination groups will receive vaccinations on Day 0, then Day 7, then Day 21. The other two vaccination groups will receive vaccinations on Day 0 and then Day 7.

9.1.4 Labeling and Packaging

Rabies Vaccine and Human Serum Albumin:

9.1.5 Product Shipment

Product will be purchased through the study team, who will be responsible for coordinating appropriate shipping and storage.

9.1.6 Product Storage

The Investigator will be personally responsible for product management or will designate a staff member to assume this responsibility.

Vaccines will be kept in the Clinical Research Unit in a secure place with restricted access. Vaccines will be stored in a refrigerator at a temperature ranging from +2°C to +8°C. The vaccine must not be frozen. The temperature must be monitored and documented for the entire time that the vaccine is at the trial site. In case of accidental freezing or disruption of the cold chain, vaccine must not be administered and must be quarantined, and the Investigator or authorized designee should contact the Novartis representative for further instructions.

9.1.7 Product Accountability

Vaccine and human serum albumin accountability will be the responsibility of the study coordinator, who will maintain both accountability logs.

9.1.8 Replacement Doses

This is an open-label trial. In the case that a dose needs to be replaced, another vial should be removed from the site's supply.

9.1.9 Disposal of Unused Products

As the vaccine used in this study is an available licensed vaccine, any unused product may be used in an additional study conducted by the PI. Any unused human serum albumin can also be used in additional studies.

10 Blinding and Code-breaking Procedures

This is an open-label trial; no code breaking procedures need to be defined.

11 Randomization and Allocation Procedures

Each subject who meets the inclusion/exclusion criteria and signs an ICF will be assigned to one of the groups based on block randomization.

Table 2: Randomization

A statistician will prepare the randomization schedule to randomly assign subject numbers to group and treatment. An appropriate blocking scheme will be used to ensure that the balance between treatment assignments is maintained. The biostatistician from the Center for Research and Evaluation will provide master randomization list to programmer with database group and label preparers starting with subject ID numbers 0001 through 0060. No other study team members will have access to this list. The study team will not know the randomization sequence.

Once the screening process is complete and the subject is eligible to be enrolled in the trial, the subject ID number will be assigned by the clinical research coordinator or designee. Subject numbers will be assigned as a 4-digit subject number (0001, 0002, 0003, etc.). The first subject randomized will be 0001, etc.

Subjects will be enrolled in six groups. When a subject is enrolled into the study, they will be allocated to a particular group and complete all vaccinations and follow-ups according to the schedule for that group.

Subject identification numbers will not be reassigned for any reason.

12 Treatment Compliance

The following measures will ensure that the vaccine doses administered comply with those planned, and that any non-compliance is documented so that it can be accounted for in the data analyses:

- All vaccinations will be administered by qualified trial personnel.
- Study Coordinator will maintain accountability records of product delivery to the trial site, product inventory at the site, dose(s) given to each subject, and the disposal of unused or wasted doses.

13 Concomitant Medications or Other Therapies

At the time of enrollment, ongoing medications including other therapies should be recorded in the source document as well as new medications prescribed for new medical conditions/AEs during trial participation.

Documentation in the eCRF of concomitant medication will include all medications listed in the source documents.

Medications will be collected in the eCRF from the day of vaccination to the end of the follow-up period in general as they may impact the response to the vaccination and impact the

consistency of the information collected on concomitant medications at any vaccination.

Medications pertaining to the contraindications list will be reported throughout the course of the trial. The information reported in the eCRF for each reported medication will be limited to:

- Trade name
- Indication
- Start and stop dates

Dosage and administration route will not be recorded.

14 Management of Samples

See the Tables of Study Procedures and Section 5.2 for details of the sampling schedule.

14.1 Sample Collection

14.1.1 Blood Samples

See the Tables of Study Procedures and Section 5.2 for details of the sampling schedule.

Immediately prior to the blood draw, the staff member performing the procedure will verify the subject's identity; will obtain the pre-printed label and the sampling stage; and will attach the label to the tube. Blood is to be taken from the limb opposite to the one that will be used for injection of the Rabies vaccine.

14.1.2 Additional Biological Samples

In the event of an AE or SAE, additional biological samples (e.g., body fluid, tissue samples) may be collected.

14.2 Sample Preparation

An overview of the lab procedures is provided here.

Antibody Assays:

At each time point, blood samples will be obtained for measurement of neutralizing antibodies against rabies virus. The blood will be allowed to clot and the serum collected by centrifugation. The serum will be stored frozen at -70°C or below until shipment to WRAIR or partner laboratory for analysis.

CMI:

Blood will be obtained for evaluation of CMI responses to vaccination. At each time point blood will be collected and PBMCs will be separated. The PBMCs will be stored frozen at -70°C or below until analyzed at SUNY Upstate or shipment to WRAIR for analysis. CMI assays will include multiparameter flow cytometry, including intracellular cytokine staining, and possibly CFSE-based proliferation assays and epitope mapping depending on the results of initial testing.

Proteomics:

Blood samples will be obtained for analysis of the proteins expressed after vaccination with Rabies vaccine. Whole blood will be collected and processed in the proteomics core lab at Upstate Medical University.

14.3 Sample Storage and Shipment

During storage, serum tubes are to be kept in a freezer whose temperature is set and maintained at -20°C or below. The temperature will be monitored and documented on the appropriate form during the entire trial. If it rises above -10°C for any period of time, the Clinical Logistics Coordinator must be notified. See the Operating Guidelines for further details.

Shipments to the laboratories will be made only after appropriate monitoring, and following notification of the Clinical Logistics Coordinator. Sera will be shipped frozen, using dry ice to maintain them in a frozen state, in the packaging container provided by the carrier. Again, temperatures will be monitored. Shipments must be compliant with the International Air Transport Association (IATA) 602 regulations.

Samples will be shipped to the Walter Reed Army Institute of Research and Kansas State University.

14.4 Future Use of Stored Serum Samples for Research

Any unused part of the research samples will be securely stored at WRAIR, or Upstate Medical University for at least 5 years.

Subjects will be asked to indicate in the ICF whether they will permit the future use of any unused samples for other tests. If they refuse permission, the samples will not be used for any testing other than that directly related to this study. If they agree to this use, they will not be paid for giving permission. (Anonymity of samples will be ensured.) The aim of any possible future research is unknown today, and may not be related to this particular study. It may be to improve the knowledge of vaccines or infectious diseases, or to improve laboratory methods. Genetic tests will never be performed on these samples without individual informed consent.

15 Clinical Supplies

The Investigator will supply all phlebotomy (with the exception of Vacutainers ®) and centrifugation equipment, including biohazard and/or safety supplies, blood collection tubes, cryotubes, cryotube storage boxes, cryotube labels, shipping containers. The biohazard and safety supplies include examination gloves, laboratory coats, and sharps disposal containers. The site will ensure that all biohazard wastes are disposed of in accordance with local practices. The Investigator will also supply appropriate space in a temperature-monitored refrigerator for the storage of the products and for the blood samples, and appropriate space in a temperature monitored freezer for serum and PBMC aliquots.

16 Endpoints and Assessment Methods

16.1 Primary Endpoints

16.1.1 Immunogenicity Endpoints

The primary endpoints for the evaluation of immunogenicity are:

- 1) Percentage of subjects in each group with titer of IgG antibodies above the protective limits (> or = 0.5 IU/ml) at 1 and 12 months after initial vaccine dose.

16.2 Secondary Endpoints

16.2.1 Immunogenicity Endpoints

- 1) Total IgG and neutralizing Ab levels, measured by ELISA and PRNT, against rabies virus at baseline and at 28 days 1 month and 365 days post-initial vaccine dose.

16.3 Assessment Methods

16.3.1 Immediate Post-vaccination Surveillance Period

Subjects will be kept under observation for 30 minutes after each Rabies vaccination to ensure their safety. Any AE that occurs during this period will be noted on the source document and identified as an immediate event / reaction; and will additionally be recorded in the eCRF.

17 Reporting AEs to IRBs

The Investigators will be responsible for informing the IRBs that reviewed the trial protocol of any reportable SAEs.

18 Reporting of Serious Adverse Events

In order to comply with current regulations on SAE reporting to health authorities, the Investigator must document all SAEs regardless of causal relationship, and notify the Sponsor within the notification timelines stated in the following sections. The Investigator will give access and provide the Sponsor and the local clinical research associate (CRA) with all necessary information to allow the Sponsor to conduct a detailed analysis of the safety of the investigational product. It is the responsibility of the Investigator to request all necessary documentation (e.g., medical records, discharge summary, autopsy) in order to provide comprehensive safety information. All relevant information must then be transcribed into the SAE form.

Timelines and process for SAE reporting

Initial reports of SAEs should be sent by the Upstate PI within 24 hours of the Investigator becoming aware of an SAE. In parallel, the Medical Monitor for the study should be notified. The Human Research Protection Office (HRPO) should also be notified via email: [contact] Human Research Protection Office (HRPO), Office of Research Protections (ORP), U.S. Army Medical Research and Materiel Command, [name] [name] 21702-5012.

Process for SAE documentation

Following receipt of SAE reports, the Sponsor may raise additional questions to ensure complete documentation of the SAEs.

Timelines and process for pregnancy reporting

If the Investigator becomes aware on pregnancy of study participant, paper pregnancy reporting form should be completed. The Investigator will notify the medical monitor email: [contact] and HRPO email: [contact] Human Research Protection Office (HRPO), Office of Research Protections (ORP), U.S. Army Medical Research and Materiel Command, [name] [name] 21702-5012.

18.1 Follow-up Reporting by the Investigator

The SAE Form completed initially must be updated within 24 hours after the Investigator has become aware of any new relevant information concerning the SAE (e.g., outcome, precise description of medical history, results of the investigation). Copies of documents (e.g., medical records, discharge summary, autopsy) may be requested

The anonymity of the subject must always be respected when forwarding this information.

18.2 Reporting of SAEs Occurring After a Subject Has Completed the Study

Any SAE that occurs after a subject has completed the study but that is likely to be related to the product or to the experiment must also be reported as soon as possible.

18.3 Assessment of Causality

The causal relationship between the SAE and the product will first be evaluated by the Investigator, using the following definitions:

0 - Not related: The AE is clearly / most probably caused by other etiologies such as an underlying condition, therapeutic intervention, or concomitant therapy; or the delay between vaccination and the onset of the SAE is incompatible with a causal relationship; or the SAE started before the first vaccination.

1 - Related: There is a “reasonable possibility” that the SAE was caused by the vaccination, meaning that there is evidence or arguments to suggest a causal relationship.

(ICH Guidelines, Clinical Safety Data Management E2A)

Following this, the Sponsor’s Product Safety Officer (PSO) will also assess the causal relationship to the product, based on the available information and current medical knowledge.

The decision to modify or discontinue the trial may be made after mutual agreement between the Sponsor and the Investigators.

18.4 Reporting SAEs to Health Authorities and IRBs

The Sponsor will inform the relevant health authorities of any reportable SAEs according to the local regulatory requirements. Reporting to the health authorities will be done according to the Sponsor’s SOPs.

The Sponsor’s Responsible Medical Officer will notify the Investigators in writing of the occurrence of any reportable SAEs. The Investigators will be responsible for informing the IRBs that reviewed the trial protocol of any reportable SAEs.

Per requirements of Department of Defense Instructions 3216.02, research funded with

Department of Defense funds requires a research monitor to be appointed. [name] will be the research monitor for this trial. His duties will include reviewing and providing and unbiased assessment and written report of all: SAEs, Subject deaths, Unexpected AEs, Protocol deviations that are related to an adverse event impacting the subject, Annual reports and Unanticipated problems involving risks to subject and others involved in the trial. The research monitor may observe recruitment and enrollment procedures and the consent process for individuals, groups or units, review monitoring plans and data collection.

The research monitor may discuss the research protocol with the investigators, interview human subjects, and consult with others outside of the study about the research. He shall have authority to stop a research protocol in progress, remove individual human subjects from a research protocol, and take whatever steps are necessary to protect the safety and well-being of human subjects until the IRB can assess the monitor's report. He shall have the responsibility to promptly report his observations and findings to the IRB or other designated official and the Human Research Protection Office.

19 Data

19.1 Data Collection and eCRF Completion

At specified intervals, the Investigator or an authorized designee will interview the subjects to collect information, and will attempt to clarify anything that is incomplete or unclear. All clinical trial information gathered by the study site will be reported electronically by the Investigator or authorized designee using a web-based eCRF. The eCRF has been designed specifically for this trial using a validated Electronic Records / Electronic Signature-compliant platform (21CFR Part 11).

Upon completion of training, each user requiring access to the EDC system will be issued a unique username and password. In the event of a change in trial personnel, each newly assigned individual will receive a unique username and password; the username and password of a previous user may not be reissued.

The Investigator is responsible for the timeliness, completeness, and accuracy of the information in the eCRFs; must provide explanations for all missing information; and must sign the eCRF using an e-signature.

19.2 Data Management

Management of Clinical Data

Data generated during the trial will be managed following two different processes:

- Clinical data, defined as all data reported in the eCRF, and laboratory data will be entered in the database held at Frontier Science in Amherst, NY.

During the trial, clinical data reported in the eCRFs will be integrated into the clinical

database under the responsibility of Upstate. Data monitoring at the sites and quality control in the form of computerized logic and / or consistency checks will be systematically applied in order to detect errors or omissions. Any questions pertaining to the reported clinical data will be submitted to the Investigator for resolution using the EDC system. Each step of this process will be monitored through the implementation of individual passwords to maintain appropriate database access and to ensure database integrity.

The validation of the immunogenicity data will be performed at the laboratory level following the laboratory's procedures. Information from the laboratory will be checked for consistency before integration into the clinical database.

After integration of all corrections in the complete set of data, the database will be released for statistical analysis.

19.3 Data Review

A review of the data is anticipated through the data review process led by Data Management before database lock.

20 Statistical Methods

The analysis will be performed under the responsibility of Upstate Medical University in conjunction with the study partners.

This will be a descriptive study to assess immunogenicity of a licensed rabies vaccine using test dosage schedules and routes of administration. No formal statistical hypothesis tests will be conducted.. Descriptive analyses for the primary endpoints will be based on per-protocol analysis data sets using the data from blood samples taken at baseline (0 days), 28 days, and 365 days after the initial dose and at 7 days after a booster at one year (372 days).. Separate descriptive analyses will be conducted for each per-protocol data set and group.

Exploratory statistical analyses of final data may be conducted, if indicated by the descriptive results. Parametric, non-parametric and resampling (bootstrapping) methods for statistical inference may be used in exploratory analyses, based on data compliance with assumptions of methods. P -values ≤ 0.05 will be considered significant and p-values ≤ 0.10 will be considered a trend. Confidence intervals will be constructed at $\alpha=0.05$ and $\alpha=0.10$. When necessary, p-value corrections for multiple comparisons will be applied.

A descriptive summary of adverse events that were reported throughout the trial will be produced. Descriptive and inferential analyses (if any) will be carried out using SAS Version 9.2 (or more recent versions), which is licensed and supplied by SAS Institute, Cary, NC, USA.

20.1 Statistical Methods for Primary Immunogenicity Objectives

Immunogenicity against rabies will be assessed descriptively using the following

parameters:

Timepoints: At baseline, 28 days and 372 days.

- Number and percentage of subjects with a titer ≥ 0.5 IU/ml against rabies virus by treatment group at days 28 and 372.

The descriptive statistics listed above will be calculated for each of the six groups for each blood draw. Descriptive results will be reported in tabular and graphic formats. A separate document, the statistical analysis plan (SAP) will be developed prior to data analysis. It will provide more detailed information about the specific descriptive statistics to be used and the format (tables, listings and figures) by which the statistics will be reported.

20.2 Statistical Methods for Secondary Immunogenicity Objectives

Immunogenicity will be assessed descriptively using the following parameters:

Timepoints: Day 28 and day 365.

The descriptive statistics listed above will be calculated for each of the six groups for the time points stated above. Specification of statistics and reporting formats will be provided in the SAP, as described above.

20.3 Per-Protocol Analysis Set

The Per-Protocol (PP) analysis set will include all subjects who had no protocol deviations at the time that the data was collected. Three PP analysis sets will be produced for the primary objective that will contain separate data from blood drawn on day 0, day 28 and day 372, respectively. Descriptive analysis of the secondary endpoint will require a fourth per protocol analysis set for blood drawn on day 365. Subjects will be excluded from the PPAS for the following reasons:

- 1) Subject did not meet all protocol-specified inclusion/exclusion criteria or definitive contraindications (only for the second and third vaccination).
- 2) Subject did not receive the correct number of injections.
- 3) Administration of vaccine was not done as per protocol (site and route of administration).
- 4) Subject did not receive vaccine in the proper time window defined in the tables of the study procedures.
- 5) Subject did not provide a post-dose serology sample in the proper time window defined in the tables of the study procedures.

Subjects will remain in this population as long as they do not meet one of the above criteria, except for blood sampling timing and validity of the serology test result*. A PP set will be defined for each injection.

*Note: For example, a subject whose time period is outside the defined visit window only between the first injection and the blood sample taken after the first injection will be excluded from PP1 but may be kept in PP2 or PP3.

Subjects will be analyzed by the vaccine group to which they were randomized, subject to the exclusion criteria above

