	
Subjects will be randomly assigned to one of the six groups through a computer generated process. A standard permuted-block design will be used for randomization/allocation in order to avoid undesirable differences in the numbers of patients assigned to each group. The randomization schedule will be generated by our statistician using SAS 9.3 PROC PLAN. Variable block sizes will be kept confidential from the protocol to reduce the predictability of the treatment assignments.
 
After screening visit, eligible subjects that are randomized will be assigned a unique subject ID. The subject ID will remain unchanged throughout the study and the nurse will confirm the number at every visit. No single subject will receive more than one subject ID. Blood will be drawn at each follow-up visit to be used in research assays for antibody response, and proteomics evaluation. See blood draw table for timing and volumes of blood draws and assays for which they will be used.
 
In all groups additional blood samples may be taken if required to assess AEs, SAEs, or abnormal laboratory findings.

--	---

Primary Objective:	Immunogenicity 1) To describe the percentage of subjects achieving a protective humoral immune response at 12 months across immunization routes at 7 days post boost.
Primary Endpoints:	Immunogenicity 1) Percentage of subjects in each group with titer of IgG antibodies above the protective limits ($>$ or $=$ 0.5 IU/ml) at 12 months, 7 days after final vaccine dose.
Secondary Objectives:	Immunogenicity 1) To describe the percentage of subjects maintaining a protective humoral immune response at 12 months across immunization routes.
Secondary Endpoint:	Immunogenicity 1) Percentage of subjects in each group with titer of IgG antibodies above the protective limits ($>$ or $=$ 0.5 IU/ml) at 12 months, prior to boost.

Exploratory Objectives	Immunogenicity 1) Describe the cell-mediated immune response to rabies vaccination in groups 1-4. 2) Proteomic characterization of the host response before and after each vaccination to identify biomarkers and correlates of immunity

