2.1 Primary Objectives

Immunogenicity

- 1) To describe percentage of subjects achieving a protective humoral immune response to each of the vaccine dosing schedules at day 28 and day 365 after first vaccine dose, and 7 days after a booster given at one year (372 days)

The endpoints for the primary objective(s) are presented in Section 16.1.

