5.3 Visit Procedures

Each of the six vaccination groups will each have a schedule of study procedures. These study procedures are described for each group separately below. Although the schedule of visits is different for each study group, the basic types of visit are the same and the same procedures will be followed.

VAC: vaccination visit at which the rabies vaccine is administered.

BL: blood sample visit at which a blood sample is obtained. These BL visits will occur at designated days or months after the previous administration of vaccine. If vaccination occurs on the same day, the blood sample will be obtained before vaccination.

All screening assessments must be completed within 60days prior to vaccination.

Screening numbers will be assigned when the subject signs the consent document starting with screening #100, 101, 102, etc. When the subject has completed the screening visit and is eligible and willing to continue participation, they will be randomized according to the randomization process outlined in section 11. Screen-fails will not be recorded in the data management system for the study. During the screening period, the following procedures and assessments will be carried out for each subject to determine their eligibility for participation in the study.

- Obtain informed consent
- Obtain medical history
- Record concomitant medications
- Record demographics
- Complete physical examination
- Review of inclusion and exclusion criteria
- Vital signs
- Urine pregnancy test (females of child bearing potential)

On Day 0, when the subject arrives for his/her first vaccination, the following events will occur before randomization:

- 1) Review informed consent
- 2) Review inclusion and exclusion criteria to confirm eligibility.
- 3) Review pertinent medical history Section 6.6 of the subject and any changes in medical history since screening.
- 4) Conduct a directed physical examination, as required Section 6.6, measure the subject's

temperature, and obtain vital signs.

- 5) For all women, obtain a urine sample and perform a urine pregnancy test prior to vaccination. Do not vaccinate if the test result is positive.
- 6) Review the subject's concomitant medications.
- 7) Record information in the source document. Concomitant medications and therapy will be recorded in the source document.

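### The primary draw 7 days after the one-year boost has a ±15-day window, and the per-protocol rule tests only that window, so it does not hold the sample to about 7 days

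*Protocol*

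**What the plan says.** The synopsis sets the primary endpoint "at 12 months, 7 days after final vaccine dose". Protocol Sections 2.1 and 20 and the SAP's Statistical Methods also place a primary sample 7 days after the one-year booster. Protocol 20.1 and the SAP's primary table analyse Day 372. Section 16.1.1 differs: it words the primary endpoint as 1 and 12 months after the initial dose and does not mention the boost.

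In the Study Procedures tables for Groups 1–4, the Day 365 boost visit and the Day 372 draw each have a window of ±15 days. Protocol 20.3 creates a separate PP set for Day 372 and excludes a subject on sample timing only if "Subject did not provide a post-dose serology sample in the proper time window defined in the tables of the study procedures". The SAP repeats this criterion and adds no narrower limit.

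The anchor of the window is not settled. Section 5.3 says of blood draws: "These BL visits will occur at designated days or months after the previous administration of vaccine". The note in 20.3 likewise gives the example of a subject "outside the defined visit window only between the first injection and the blood sample taken after the first injection". Both point to the last injection. The tables, however, head their columns by Study Day.

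**The concern.** The Day 372 percentage is meant to describe the response 7 days after the boost. A PP set should keep samples that measure that time point and remove those that do not. Here the rule admits lags far from 7 days, and under one reading it can remove a lag close to 7.

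The case that matters most is an early draw in a subject whose titer had fallen below 0.5 IU/ml by Day 365. Section 1.5 foresees such subjects. A sample taken a day or so after the boost could still reflect persistence before the boost, which is the synopsis's secondary endpoint, while being counted under the primary one.

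The opening sentence of 20.3, which limits the set to "all subjects who had no protocol deviations at the time that the data was collected", does not close the gap. A draw inside its table window is not a deviation.

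**Working it through.** **Inputs.** Boost Day 365 ±15 and draw Day 372 ±15 (Study Procedures tables, Groups 1–4). Other windows from the same tables: Day 7 ±1, Day 14 ±1, Day 21 ±1 and Day 28 ±2. From Section 5.3: "If vaccination occurs on the same day, the blood sample will be obtained before vaccination". A same-day draw is therefore pre-dose, and the earliest post-boost sample is day 1.

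**The plan's own figure.** 365 + 7 = 372, which reproduces the nominal draw day.

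**Boost as anchor.** Lag = 7 ± 15, that is 7 − 15 = −8 to 7 + 15 = 22. Criterion 5 concerns a post-dose sample, so the usable range is 1 to 22 days.

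**Study Day as anchor.** The boost may fall on Days 350–380 (365 ± 15) and the draw on Days 357–387 (372 ± 15). Lag = draw day − boost day, at least 1.

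- Boost on Day 350: 357 − 350 = 7 to 387 − 350 = 37 days.
- Boost on Day 365: 357 − 365 = −8, cut to 1, to 387 − 365 = 22 days.
- Boost on Day 380: 357 − 380 = −23, cut to 1, to 387 − 380 = 7 days.

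Over all allowed boost days the accepted lags run from 1 to 37 days. An 8-day lag after a Day 380 boost falls on Day 388, past Day 387, and is rejected.

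**The protocol's other draws 7 days after a dose.**

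| Draw | Preceding dose | Accepted lag, last dose as anchor (days) | Accepted lag, Study Day as anchor (days) |
|---|---|---|---|
| Day 7 ±1 | Day 0 | 6–8 | 6–8 |
| Day 14 ±1 | Day 7 ±1 | 6–8 | 13 − 8 = 5 to 15 − 6 = 9 |
| Day 28 ±2 (Groups 1–2) | Day 21 ±1 | 5–9 | 26 − 22 = 4 to 30 − 20 = 10 |
| Day 372 ±15 | Day 365 ±15 | 1–22 | 1–37 |

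**Carry-forward reading.** 350 + 7 = 357 and 380 + 7 = 387, so the draw window is exactly the boost window moved by 7 days. That fits an intention to let the draw follow a shifted boost. It still leaves the tolerance around 7 days unstated.

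**The case against.** The strongest reply is that the second ±15 merely accommodates a boost given early or late, with the 7-day interval understood. The exact 7-day shift between the two windows supports this, and a boost-anchored window that opens 8 days before the dose is awkward. This reading is plausible, but it is written nowhere, and criterion 5 points to the tables alone.

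The comparators are also imperfect. Day 7 is itself a vaccination visit in Groups 1–4. Day 28 is 7 days after a dose only in Groups 1–2; in Groups 3–4 it falls 21 days after the Day 7 dose. The windows widen with elapsed time (±1, ±2, ±7, ±15). So ±1 or ±2 is a guide to what the protocol treats as close to 7 days, not a requirement for a visit a year later.

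Timing matters too. The SAP is dated 05 December 2016, while the protocol's approximate calendar puts the last visit in February 2016 and completion of assays in July 2016. If that calendar held, draw dates and titers existed before this SAP version. Narrowing the PP window then would retrospectively exclude subjects who met the protocol's windows, in open-label groups of 12. That objection stands, and it shapes the fix.

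A reader might infer that the Day 372 percentages are biased or that one regimen gains. The documents do not support this. The windows are the same in Groups 1–4, nothing shows how often very early or late draws would occur, and Section 1.5 speaks of a rapid and robust return of titers after one booster. The study is descriptive, with no formal hypothesis test at stake.

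**Conclusion.** The point holds as a mismatch between a stated time point and the rule meant to enforce it. Under either written anchor the Day 372 PP set accepts lags well away from 7 days: 1–22 with the boost as anchor, 1–37 by Study Day. Under Study Day it can also refuse an 8-day lag. This goes beyond missing detail, because the rule as written admits samples that do not measure the stated time point.

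The lag ranges are what the rule allows, not expected frequencies, and no change in the percentage at or above 0.5 IU/ml is claimed. The conclusion assumes that Day 372 is a primary time point. Most sections and the SAP say so, but Section 16.1.1 does not and should be reconciled with them. It would be wrong to conclude that ±15 is necessarily a mistake, or that the documents require ±1 or ±2.

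**What to change.** 1. Reconcile the Study Procedures tables with Section 5.3 and the note in 20.3 by stating the anchor of the draw window. Reconcile Section 16.1.1 with the other statements of the primary endpoint.
2. In protocol 20.3 and the SAP, define criterion 5 for the Day 372 set by days since the boost actually given, with a stated tolerance around 7 days fixed without reference to the titers. The ±1 or ±2 of the other 7-day post-dose draws may serve as a guide.
3. List actual days since boost by subject.
4. If draw dates and titers already exist, keep the PP set on the protocol windows, say which anchor was applied, and report the Day 372 percentage limited to draws near 7 days after the boost as a supporting analysis labelled post hoc.

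A Day 372 percentage in the full analysis set (FAS), limited to valid samples drawn after the boost, is optional. It would be a small addition, since the FAS is now planned only for the kinetic analysis. No change to the vaccination window is proposed.

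**Cost.** A wording change and one listing. PP criteria 4 and 5 already require both the vaccination and the sample dates. The downside of a tighter criterion is a smaller denominator: each excluded subject is 1/12 = 8.3% of a full group, withdrawn subjects are not replaced (Section 6.8) and missing data are not imputed (Section 21.1).
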